- Sedentary older Latinos randomly assigned to the health education control group will participate in classes developed for older adults and offered by the University of Illinois Extension for the past 10 years. All classes are conducted in Spanish by extension staff using Spanish-language materials. The curriculum covers topics such as heart disease, diabetes, cancer, stress, asthma, osteoporosis, immunizations, home safety, and sexual health. Classes will meet one day per week for two hours, to provide equitable social contact as the treatment group.
- If participants are put into the health education program, they will be offered a short, 4-session dance program during the additional 4-month period, consisting of one class for each of the four styles of dance taught in the larger BAILAMOS© dance program.
- For the dance group and the health education group, separate lotteries will occur during the initial 4-month program and the follow-up 4-month maintenance program. All participants who meet criteria of having attended 75% of classes over each 4-week period are eligible for the lottery. One lottery will happen every four weeks (four lotteries total for the initial 4-month program and four lotteries for the follow-up 4-month maintenance program), and two participants from the dance group will win \$50 and two participants from the health education group will win \$50 for each lottery. All participants who are eligible will have an equal chance of winning, and the odds of winning are dependent upon the number of participants who meet lottery eligibility criteria (for example, if 10 participants are eligible, you have a 1/10 or 10% chance of winning). For each lottery, if you are eligible, your name will be put into a hat; the winner will be randomly drawn from the hat; your name will not be linked to research data; and the names will be destroyed immediately after the lottery occurs.
- At 4-months post-intervention, and at 8-months, testing will occur. Questionnaires and tests will be administered in the same order as baseline and 4-month testing.
- After the PRE-intervention testing (baseline/month 0) a \$10 cash gift will be provided, and participants will be asked to wear an accelerometer for 7 days. When that accelerometer is returned, participants will receive another \$10 cash gift.

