- After the initial 4-month program, testing will occur. After this POST-intervention testing (month 4), a \$10 cash gift will be provided, and participants will be asked to wear an accelerometer for 7 days. When that accelerometer is returned, participants will receive another \$10 cash gift.
- After the maintenance 4-month program for dancers, testing will occur for both participants from the dance group and the health education group. At this month 8 testing, a \$10 cash gift will be provided, and participants will be asked to wear an accelerometer for 7 days. When that accelerometer is returned, participants will receive another \$10 cash gift. Thus, a total of \$60 is possible.
- Through Amendment # 16, we would like to allow research participants in the maintenance component of the program to invite 1 or 2 family member(s) or friend(s) to come dance with them. Both of the sites which are in the maintenance phase of the program are struggling with attendance adherence.

The person our participant invites will not be involved with any of the study procedures, such as:

- No visits to the University of Illinois at Chicago for questionnaires (No data collected on them)
- No need to wear accelerometer
- Not eligible for lotteries
- Not eligible for compensation

In addition, in order to attend a dance session, the person will need to:

- Be 55 years or older
- Be able to speak English and/or Spanish
- Not be in the Health Education group of the study
- Be physically able to dance (no assistive devices permitted like canes, walkers, or wheelchairs)
- Sign a one-time waiver
- Sign-in at each class attended

The investigator may stop a person from participating in the dance sessions of the maintenance program if the person is at risk of injury, or if he/she is disruptive or inappropriate during any session.

Emergency Procedures for Study Participant

In the event of an emergency, staff responds quickly and calmly.

All emergencies are documented in the participant's file and if the project coordinator is not onsite, she is notified immediately by the Indigenous Leader (Participant Leader). The emergency is brought to the attention of the Principal Investigator by the Project Coordinator, so he is aware of the problem and can discuss how to prevent future emergencies. In addition, the Project Coordinator files an adverse report form with IRB

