(Institutional Review Board Office), stating nature of incident, extent of injury and reports participant injured by name and ID number.

Medical Emergencies for Study Participant

In the event of a medical emergency, staff responds quickly and calmly. The Project Coordinator is notified of the emergency by the Indigenous Leader (Study Participant), Project Coordinator notifies Principal Investigator. If a serious medical emergency arises, the Indigenous Leader (Study Participant) calls 911 and notifies participant's emergency contact. In addition, the Project Coordinator files an adverse report form with IRB (Institutional Review Board Office), stating nature of incident, extent of injury and reports participant injured by name and ID number.

Emergency Procedures for "Invitees":

In the event of an emergency, "Invitees" will follow the site protocol. The Indigenous Leader (Study Participant) responds quickly and calmly, following the site protocol for emergencies. The emergency is brought to the attention of the Project Coordinator. Project Coordinator notifies the Principal Investigator, so he is aware of the problem and can discuss how to prevent future emergencies.

Medical Emergencies for "Invitees"

In the event of a medical emergency, Indigenous Leader (Study Participant) responds quickly and calmly, following site protocol, which is to call 911. Indigenous Leader (Study Participant) notifies Project Coordinator and Principal Investigator.

Below are the medical emergency procedures for our current sites:

- West Town Satellite Senior Center: Notify Senior Center Coordinator, who will then make Security aware of situation, and if necessary, Security will call 911 and make an incident report.
- Pilsen Satellite Senior Center: Call 911 and notify emergency contact/family member on record, center Coordinator will file incident report.
- Kelvyn Park Satellite Senior Center: Call 911 and notify emergency contact/family member on record, center Coordinator will file incident report

Under Amendment #18, we added a short survey for Senior Center directors to be collected at 1-month and 6-months after the Maintenance program ends to see if people are still dancing, and to get Directors' thoughts, feelings, and perceptions of the program's sustainability.

Under Amendment #21, we propose to audiotape the Senior Center Director's responses to our Questionnaire (previously approved under Amendment #18). This will allow us to

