- b. Emergency contact information will be collected at baseline. Should an injury or any other adverse event occur, we will contact the emergency contact person immediately, followed by the UIC IRB, and the program officer assigned to this grant.
- c. We will tell participants that should they become injured due to dancing, they should notify the dance leader and/or research assistants in attendance and to consult their physician if necessary.
- d. If a participant injures him/herself and/or falls, we will assess and treat with first aid.
- e. If there are medical facilities and/or medical personnel available at the research site, we will inform them and request assistance, and also follow the stated protocols and procedures of the site. For those sites without medical facilities, we will follow the stated protocols and procedures of the site.
- f. If needed, we will arrange for transport to the emergency room.

Adverse events will be tracked and categorized as "serious" (for example illness requiring hospitalization, or events deemed life-threatening) or "minor" adverse events. Serious events will be reported to the IRB immediately, whereas minor adverse events will be documented in the annual summary sent to the IRB.

h. Data management

To maintain confidentiality, all participants will be assigned an identification number (ID). Only the ID appears on the questionnaire and other study documents. There is no identifying information on the questionnaire. The ID and participant's name are kept on a password protected computer.

Screening, tracking of participants, etc. will be done using Study360 software described in detail in the Initial Review Application. In short, Study 360TM (Almedtrac, Inc.) is a multi-component, web accessible software system designed to reduce management burden, increase efficiency and improve visibility of clinical trials. It is a highly secure application that uses a 128-bit SSL with third party certificate authority encryption mechanism. Data are maintained and stored in an Oracle 10g RDBMS running in a secure environment on a Dell PowerEdge server running Windows Server 2003 in Entity-Attribute-Value (EAV) format. Data in the Oracle database are maintained in original and unedited format and the research team has the ability to connect to a view that is custom-designed for the project for the purpose of downloading a snapshot of the data into SPSS via an ODBC connection.

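### The protocol gives no method for collecting adverse events, its one prompt to participants covers only dance injuries, and its IRB routes for minor events differ

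*Combined protocol and SAP*

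**What the plan says.** **Collection.** The general statement closing Section 4.g is not limited by arm or cause: "Adverse events will be tracked and categorized as" serious or minor. No form, question, recall period or schedule follows. The only instruction addressed to participants is item 2c under the handling of injuries: "should they become injured due to dancing, they should notify the dance leader and/or research assistants in attendance". Section 4.e describes testing at baseline, month 4 and month 8 with interviewer-administered questionnaires, but mentions no adverse event question. Section 4.f contains no adverse event summary or comparison.

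**Contact.** Dance classes are twice weekly in both 4-month periods (Sections 3 and 4.e). Health education classes are weekly and last two hours. In the second period control participants also have a dance offer: "they will be offered a short, 4-session dance program during the additional 4-month period". The text does not say whether their weekly classes continue.

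**IRB reporting.** Three statements apply:
- Section 4.g, item 2b: "Should an injury or any other adverse event occur, we will contact the emergency contact person immediately, followed by the UIC IRB", and then the program officer.
- Section 4.g, closing paragraph: "Serious events will be reported to the IRB immediately, whereas minor adverse events will be documented in the annual summary sent to the IRB".
- Section 4.e, emergency procedures for study participants: "the Project Coordinator files an adverse report form with IRB", with no split into serious and minor.

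**The concern.** The trial gives a new physical activity to sedentary older adults at risk for disability, and Section 4.g itself lists strains, falls and, rarely, cardiac irregularities as possible harms. The safety evidence it cites is a single-group pilot of 12 people, 9 of whom completed. A randomised control arm of 166 could show whether falls and injuries are more or less frequent with the programme, but only if events are sought in the same way in both arms.

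As written, the one prompt depends on the participant attributing the injury to dancing and telling someone present at class. No matching prompt covers the health education classes, a fall at home or an illness. An excess of events in the dance arm could then reflect better detection, and a low count in either arm could reflect missed events.

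The reporting routes are a separate matter. Staff faced with a minor sprain cannot tell from the text whether it calls for a contact with the IRB for that event, an entry in the annual summary, or both.

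**Working it through.** The plan states no adverse event rate and no safety sample size, so there is no figure of its own to reproduce. The check has three parts.

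**1. Scheduled class contacts**

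Weeks per period: Section 3 gives 32 dance sessions in 4 months at two per week, so 32 / 2 = 16 weeks. The lottery schedule in Section 4.e (four lotteries, one every four weeks) gives the same: 4 × 4 = 16.

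| Period | Dance | Control, classes stop at month 4 | Control, classes continue |
|---|---|---|---|
| Months 1–4 | 2 × 16 = 32 | 16 | 16 |
| Months 5–8 | 2 × 16 = 32 | 4 | 16 + 4 = 20 |
| Total | 64 | 20 | 36 |
| Ratio, dance to control, 8 months | – | 64 / 20 = 3.2 | 64 / 36 = 1.8 |
| Ratio, months 5–8 | – | 32 / 4 = 8 | 32 / 20 = 1.6 |

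In months 1–4 the ratio is 32 / 16 = 2 in either case. These are ratios of occasions for contact, not of captured events.

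**2. What unequal detection could do (illustration only)**

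Assumptions, none of them from the documents: the same true risk p of at least one event in both arms, and detection of 90% in dance and d in control. The sample size is the documents' 166 per arm. The expected number of participants with a recorded event is 166 × p × detection. The apparent risk ratio is 0.90 / d, because p cancels.

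The chance of a false significant difference uses the normal approximation for two proportions, two-sided 5%: Φ[(|p1 − p2| − 1.96 × se0) / se1], with se0 the pooled and se1 the unpooled standard error. For p = 20% and d = 60%: p1 = 0.18, p2 = 0.12, se0 = √(0.15 × 0.85 × 2/166) = 0.0392, se1 = √[(0.18 × 0.82 + 0.12 × 0.88)/166] = 0.0391. Then (0.06 − 0.0768) / 0.0391 = −0.43, which gives 33%.

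| Control detection | Expected counts at p = 20% | Apparent risk ratio | False significance, p = 10% | p = 20% | p = 30% |
|---|---|---|---|---|---|
| 90% | 30 v 30 | 1.0 | 5% | 5% | 5% |
| 60% | 30 v 20 | 1.5 | 18% | 33% | 50% |
| 45% | 30 v 15 | 2.0 | 37% | 67% | 87% |
| 30% | 30 v 10 | 3.0 | 64% | 92% | 99% |

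The table shows what the bias could be, not what it is.

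**3. Route to the IRB for one minor injury in class**

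- Item 2b applies, because it covers any injury or other adverse event with no severity threshold. It sets a contact with the IRB for that event.
- The closing paragraph applies, because the event is minor. It places the event in the annual summary and contrasts this with immediate reporting of serious events.
- If staff treat the incident as an emergency, the Section 4.e form also applies, whatever the severity.

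The same event therefore has two routes, or three if it is handled as an emergency, and no statement says which governs.

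**The case against.** **Item 2c is an injury-response instruction, not the collection plan.** It sits in a list on handling injuries, while the tracking statement covers both arms, and its example of a serious event (an illness leading to hospital admission) is not tied to dancing. The questionnaires are not reproduced, and software tracking is detailed in an application outside these documents. This stands. A reader might infer that events are captured mainly through class contact, but that would be drawn from silence. The documents support only that the method is unspecified and that the one stated prompt concerns dancing.

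**The contact ratios can be over-read.** The figures 3.2 and 8 assume that health classes stop at month 4. Lotteries for the health education group also run in the second period and depend on class attendance, which suggests that classes may continue; the ratios are then 1.8 and 1.6. Capture need not be proportional to contacts either, since an injury can be mentioned at the next class, and the two-hour control classes are meant to equalise social contact. All of this stands, so neither set of ratios estimates the inflation in event counts.

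**No comparison of safety between arms is planned.** This is correct, and no planned analysis is in error. The point is about what the trial could credibly report on harms.

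**The IRB statements can be read together.** In item 2b the word for immediacy attaches to the emergency contact and the IRB comes next in order. A minor event could be both notified and listed annually, so it would go too far to say that the rules cannot both be followed. Even so, item 2b sets a contact for each event that the annual-summary rule does not, and the contrast in the closing paragraph implies different routes.

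**Conclusion.** The point holds as a gap in specification, together with a separate inconsistency in reporting.

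The adverse event collection method is not stated, the only participant prompt is specific to dancing, and scheduled contact favours the dance arm by 1.8 to 3.2 times over 8 months (1.6 to 8 times in months 5–8), depending on whether health classes continue. Any by-arm description of falls or injuries would be open to ascertainment bias, and events outside class may be missed in both arms. The size of the bias is unknown: the apparent risk ratios of 1.5 to 3.0 in the illustration rest on assumed detection shares and an assumed equal true risk.

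A reader might go further and conclude that counts are not comparable between arms. The documents do not establish that; unequal capture is a plausible consequence of the design, not a stated feature of it.

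The differing IRB routes for minor events are on the page and need to be reconciled. They affect how and when an event is reported, and give no reason for counts to differ by arm.

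**What to change.** 1. Add the same short questions on falls, injuries and hospitalisation since the last visit to the existing month 4 and month 8 interviews in both arms, regardless of supposed cause.
2. Protect the assessors, who under Section 4.e are not told the group. Either ask these questions after all outcome measures at the visit are complete and without asking where the event happened, or have staff who do not assess outcomes ask them. The second is safer if the same assessor may test a participant at both visits, because something learned at the end of month 4 could carry over to month 8.
3. Tabulate the answers by arm as randomised, and list class-reported events separately.
4. State whether health education classes continue in months 5–8, so that the difference in contact can be described.
5. Reconcile item 2b, the closing paragraph of Section 4.g and the emergency procedures in Section 4.e into one rule for reporting minor events to the IRB. Which rule should apply is for the investigator and the IRB to settle.

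The cost is a few minutes of interview time at visits already planned, one table and a text correction. The downsides are recall error over 4 months and some remaining risk of unblinding assessors.
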